**Please note that this study will not be using separate toxicity scales for acute and late radiation adverse events.**

## **10 DATA COLLECTION**

### **10.1 Submission**

10.1.1 Data should be submitted to:

**Department of Radiation Oncology  
Clinical Research Office  
The University of Texas Southwestern Medical Center  
Attention: [name], Project Manager  
[name]  
[name]  
[contact]**

Patients will be identified only by initials (first middle last) and a unique study ID number assigned to each study participant; if there is no middle initial, a hyphen will be used (first-last). Last names with apostrophes will be identified by the first letter of the last name. Participating sub-sites must remove or black-out identifiers from source documentation that is sent to UTSW.

#### 10.1.2 Summary of Data Submission

| Item   | Due   |
|---|--|
| Demographics  | Within 2 weeks of study entry  |
| Eligibility and Entry Characteristics including baseline H&P and labs | Within 2 weeks of study entry  |
| Baseline Humphrey Visual field testing                                | Within 2 weeks of study entry  |
| Baseline audiology  | Within 2 weeks of study entry  |
| Baseline Neurocognitive Assessments                                   | Within 2 weeks of study entry  |
| Baseline QOL Assessments  | Within 2 weeks of study entry  |
| Dosimetry information   | Within 1 week after completion of post-implant CT imaging  |
| Follow-up H&P data  | follow-up at 1, 3, 6, 9, 12 months, then every 6 months to 4 years; then annually for years 4-10     |
| Adenoma Measurements  | follow-up at 3, 6, 9, 12 months, then every 6 months to 4 years; then annually for years 4-10        |
| Follow-up Humphrey Visual field testing                               | follow-up at every 6 months to 2 years; then annually for years 2-10                                 |
| Follow-up Endocrine Evaluation  | follow-up at every 12 months to 10 years   |
| Follow-up Neurocognitive Assessment                                   | follow-up at every 12 months to 10 years   |
| QOL Assessment  | follow-up at every 6 months to 1 year, then annually for years to 2-10                               |
| Adverse Event assessment  | follow-up at 1, 3, 6, 9, and 12 months, then every 6 months to 4 years; then annually for years 4-10 |

## 11 STATISTICAL CONSIDERATIONS

### 11.1 Primary Endpoint

11.1.1 The primary endpoint of this study is to determine the rate of partial (>30% reduction in GTV) or complete responses occurring within one year of therapy. This will be assessed by measuring the adenoma in three dimensions, as well as determining the total volume, on pre-treatment and follow-up imaging studies. The percent change in size and volume of the adenoma will then be calculated by subtracting the post-treatment measurements from the pre-treatment measurements then divided by the pre-treatment measurements and then multiplied by 100. The mean, median and standard deviation of the percent change will be determined.

### 11.2 Secondary Endpoints

#### 11.2.1 Change in Humphrey Visual Fields

11.2.1.1 Data for each eye will be obtained before and after treatment. Visual fields will be reviewed by a neuro-ophthalmologist for any signs of improvement or deterioration.

#### 11.2.2 Toxicities

11.2.2.1 Specific toxicities that will be monitored are cerebrospinal fluid rhinorrhea, radiation-induced necrosis, changes in visual field deficits, changes in visual acuity, changes in auditory acuity, worsening headaches, and development of neurocognitive and/or short-term memory deficits

#### 11.2.3 Progression Free Survival

#### 11.2.4 Change in QOL Assessments

11.2.4.1 Scoring of each assessment tool will be conducted as per each individual tool's scoring instructions

11.3 Sample Size

11.3.1 **Overview:** The primary goal of this study is to monitor shrinkage in adenoma size and volume following treatment.

11.3.2 **Sample Size Derivation:** The predicted partial or complete response rate (PR+CR) of treated subjects at a follow-up interval of 12 months is the determinant of sample size. A PR + CR rate of 10% or less would be considered insufficiently low for further investigation of this treatment, whereas a PR + CR probability of 50% or higher will be considered worthy of future investigation. If the true PR + CR rate is 50%, a sample size of 10 patients will provide 87% power to detect a significantly higher RTS than 10% with an alpha level of 0.025. To assure an adequate number of evaluable patients, allowing for a small number of patients who would be lost to follow-up or otherwise found non evaluable, a total of up to 12 patients will be enrolled. This analysis applies to both cohorts (those with and without previous radiation therapy)

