## 1.5 **Description of protocol therapy**

- 1.5.1 This study is a single arm Phase II pilot trial. Patients enrolled on the trial will undergo implantation of high activity iodine-125 seeds into their pituitary adenoma as outlined in sections 6 and 7. The tumor response to treatment will be monitored as well as change in visual fields, associated adverse effects, progression free survival and patient reported outcomes.

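### The 87% power stated for 10 patients is not attainable at one-sided alpha 0.025: the exact test gives 82.8%, and no test, sidedness or required number of responders is written down

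*Combined protocol and SAP*

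**What the plan says.** Section 1.5.1 describes the design: "This study is a single arm Phase II pilot trial". The comparison is therefore of one sample with a fixed rate.

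Section 11.3.2 sets that rate: "A PR + CR rate of 10% or less would be considered insufficiently low for further investigation of this treatment". A rate of 50% or more is taken as worth pursuing. On that basis, "a sample size of 10 patients will provide 87% power to detect a significantly higher RTS than 10% with an alpha level of 0.025". To allow for patients who are lost or cannot be evaluated, "a total of up to 12 patients will be enrolled", and the reasoning is carried over to patients with and without earlier radiotherapy: "This analysis applies to both cohorts".

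Section 11.1.1 names the response rate within one year as the primary endpoint and defines a patient's response (more than 30% reduction in GTV, or complete response). The analysis it then describes is of percent change: "The mean, median and standard deviation of the percent change will be determined". Section 11.5.1.2 repeats that summary. Neither section tests the response rate against 10% or gives a number of responders that counts as success.

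**The concern.** With 10 patients and a yes/no outcome, only a few decision rules exist, and each has a fixed size and power. A stated power should match one of them, or be explained by a named approximation. The 87% does neither.

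Two things are at stake. First, this is the only power statement and it serves both cohorts. At exactly 10 evaluable patients, the chance of missing a true 50% response rate is 17.2% rather than 13%. Second, the plan sets go/no-go rates but not the responder count that separates them. Because the test is unnamed and the evaluable number can vary, that count could be settled after the results are known.

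**Working it through.** **Inputs** (all from 11.3.2 unless noted)

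- Null rate p0 = 0.10; alternative p1 = 0.50
- Evaluable patients n = 10 per cohort, up to 12 enrolled
- Alpha = 0.025; stated power 87%
- Single arm (1.5.1)
- Sidedness not stated. One-sided is assumed, because the plan speaks of detecting a higher rate.

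**Step 1. Exact rules at n = 10.** For a rule of r or more responders, size = P(X ≥ r | p = 0.10) and power = P(X ≥ r | p = 0.50), with X binomial(10, p).

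| Rule | Size | Power |
|---|---|---|
| 3 or more | 7.02% | 94.5% |
| 4 or more | 1.28% | 82.8% |
| 5 or more | 0.16% | 62.3% |

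No rule gives 87%. Among those with size at or below 2.5%, the best is 4 or more, with power 82.8%.

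**Step 2. Upper bound for any test at level 0.025.** The most powerful test adds a randomised rejection at X = 3 to use up the remaining alpha.

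- P(X = 3 | 0.10) = 0.0574 and P(X = 3 | 0.50) = 0.1172
- Rejection probability at X = 3: (0.025 − 0.0128)/0.0574 = 0.2126 (from unrounded values)
- Power: 0.8281 + 0.2126 × 0.1172 = 0.853

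To reach 87%, the rejection probability at X = 3 would have to be (0.87 − 0.8281)/0.1172 = 0.357. The size would then be 0.0128 + 0.357 × 0.0574 = 0.033.

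**Step 3. Can an approximation give 87%?** The usual formula is power = Φ[(p1 − p0 − c − z·se0)/se1], with se0 = √(0.1 × 0.9/10) = 0.0949, se1 = √(0.5 × 0.5/10) = 0.1581, and c = 0 or, with continuity correction, 1/(2n) = 0.05.

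| Version | Nominal power | Rule it implies | Exact size | Exact power |
|---|---|---|---|---|
| One-sided 0.025, c = 0: Φ[(0.4 − 1.960 × 0.0949)/0.1581] | 91.2% | 3 or more | 7.02% | 94.5% |
| One-sided 0.025, c = 0.05 | 85.0% | 4 or more | 1.28% | 82.8% |
| Two-sided 0.025 (z = 2.241), c = 0 | 88.2% | 4 or more | 1.28% | 82.8% |
| Two-sided 0.025, c = 0.05 | 80.8% | 4 or more | 1.28% | 82.8% |

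Other one-sided variants give 83.5% (arcsine) and 71.6% (Wald). None equals 87%. The two nearest, 85.0% and 88.2%, both reject at 4 of 10, so their actual power is 82.8%. With one responder expected under the null (10 × 0.10), large-sample formulas are unreliable here.

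An exact two-sided reading makes matters worse. With 0.0125 in the upper tail, 4 of 10 (1.28%) just fails, the cutoff becomes 5, and power is 62.3%.

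**Step 4. Other evaluable numbers, one-sided 0.025.**

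| Evaluable | Cutoff | Size | Power |
|---|---|---|---|
| 10 | 4 | 1.28% | 82.8% |
| 11 | 4 | 1.85% | 88.7% |
| 12 | 5 | 0.43% | 80.6% |
| 12 (one lower) | 4 | 2.56% | 92.7% |

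Four responders of 12 misses the alpha limit by 0.06 percentage points. This is the result on which an unwritten rule matters most.

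**Step 5. Do the two extra patients restore 87%?** The plan gives no loss rate, so independent losses are assumed. Power is averaged over the resulting evaluable number, using the full exact cutoff table, including numbers below 10 (4 at 7 to 9 evaluable, 3 at 5 or 6).

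| Assumed loss | Enrol 12 | Enrol 10 |
|---|---|---|
| 0% | 80.6% | 82.8% |
| 5% | 83.4% | 78.4% |
| 10% | 83.2% | 73.8% |
| 16.7% | 79.7% | 68.0% |

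The extra patients protect power once losses occur, but the average for 12 enrolled peaks at 83.6% (at 6.9% loss) and does not reach 87%.

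**The case against.** The strongest reply is that the plan never says its calculation was exact. Nominal approximations lie on both sides of 87% (85.0% and 88.2%), so the figure may come from an approximation rather than a slip. That is possible, but it does not rescue the statement, because both of those tests reject at 4 of 10 and so have 82.8% power. The conclusion should be read as applying to tests whose true size is at most 0.025.

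A second reply is that the null, alternative, alpha and direction are all fixed, so an exact one-sided test has one full-level cutoff for each evaluable number and little is left to choose. This holds once the test is named. Since it is not, a post hoc choice is possible, though not certain. The patient-level 30% threshold is also defined; only the trial-level count is missing.

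A third reply is that the gap is 4.2 points in a small Phase II pilot, that power stays above 80% at 10, 11 and 12 evaluable patients, and that at 11 it exceeds the stated figure. All of this stands. The power misstatement alone would be minor; the missing decision rule gives the point most of its weight.

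**Conclusion.** The statement is wrong as written. At 10 evaluable patients, with a one-sided test of true size no more than 0.025, power against a 50% response rate is 82.8%, not 87%, and no such test can exceed 85.3%. The plan also lacks a named test, its sidedness and the number of responders required, and nothing elsewhere in the document supplies them.

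The severity is moderate. Neither cohort needs more patients: exact power is 82.8%, 88.7% and 80.6% at 10, 11 and 12 evaluable, with size at most 1.9%. The result rests on the one-sided reading; an exact two-sided reading would lower power further. The averages over losses rest on assumed loss rates, and the conclusion does not depend on them.

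**What to change.** Rewrite the power statement in 11.3.2 along these lines: *In each cohort, a one-sided exact binomial test of the PR+CR rate, null 10%, alternative 50%, alpha 0.025. Success is 4 or more responders among 10 or 11 evaluable patients, or 5 or more among 12. Power is 83%, 89% and 81% respectively; actual size is at most 1.9%.*

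If fewer than 10 are evaluable, the same test fixes the cutoff (4 at 7 to 9, 3 at 5 or 6). It is worth printing the full table, since under an assumed 10% loss about 11% of cohorts of 12 would fall below 10.

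An alternative is to require 4 or more responders at any evaluable number from 10 to 12 and restate alpha as 0.026, with power from 83% to 93%. This avoids the drop in power from 88.7% to 80.6% when the twelfth patient is evaluable. The choice is the sponsor's, and should be made before the data are seen.

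In either case, put the rule into 11.1.1 and 11.5.1.2 beside the descriptive summaries, and replace RTS, which is undefined and appears to mean the PR+CR rate.

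The cost is wording only, with no added patients. The stated power at 10 patients falls from 87% to 83%; under the alternative, alpha also becomes 0.026.

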## **STUDY SYNOPSIS**

### **Interstitial Radioactive Iodine Implants for the Treatment of Pituitary Macroadenomas**

#### Schema

#### **Patient Population:** (See Section 3.0 for Eligibility)

Patients must have biopsy proven pan-invasive pituitary macroadenomas of the pituitary gland. Pan-invasive for the purposes of the protocol will be defined as meeting each of the following 2 major criteria:

1. tumor volume greater than 20 cc at enrollment, and
2. suprasellar extension.

In addition, a pan-invasive tumor must meet any one of the following 3 minor criteria:

- a) unresectable tumor invasion into a cavernous sinus,
- b) bone or bone marrow invasion into the clivus or temporal bones, or
- c) tumor extension in any direction unlikely to be completely removed specifically by a transphenoidal surgical approach.

Patients who meet the two major criteria above (1 and 2) and are medically inoperable for tumor resection (due to confounding co-existing medical problems) are eligible without meeting any of the three minor criteria (a, b, or c).

Patients should be immediately threatened for vision loss or other significant neurological impairment directly related to tumor mass effect. As such, all patients enrolled would likely benefit from tumor response (shrinkage).

Patients with pituitary carcinomas are not eligible.

Number of patients = up to 12 in each or two cohorts listed below (total up to 24).

Patients will be divided into two cohorts depending on if they have been previously treated with radiotherapy or not.

Eligible patients may have a functioning or non-functioning adenoma and may have previously undergone a surgical resection for their adenoma.

The goal of the study is primarily to monitor for tumor shrinkage after seed implantation. Additional outcomes that will be monitored are change in visual fields, potential toxicities (acute and late) related to the treatment, progression free survival, and changes in patient reported outcomes.

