## **INTRODUCTION**

### **1.1 Epidemiology**

1.1.1 Pituitary adenomas constitute 10-20% of all central nervous system tumors. Patients with secretory adenomas most frequently present with endocrinopathies; the goal of therapy in these cases is normalizing the endocrinopathy and eliminating further lesion growth. First-line therapy can be either medical or surgical depending on the hormone being secreted. Thirty percent of pituitary adenomas are nonsecretory and present clinically due to their progressive increase in size and the mass effect exerted on the surrounding tissues, most commonly, the optic apparatus. Controlling tumor growth and preserving vision are the most important factors in the treatment of nonsecreting adenomas. Surgery is considered first-line treatment for these tumors.

Tumors with their greatest diameter of less than 10mm are classified as “microadenoma”, whereas those with a diameter of 10mm or more are considered “macroadenomas”. Due to their benign nature and variable clinical presentation, pituitary adenomas may become very large, a factor that complicates treatment. Widespread surgical and radiologic interest in these tumors has resulted in various definitions of pan-invasive or “giant” pituitary adenomas. Both Fisher et al. and Symon et al. defined giant adenomas as those showing suprasellar extension of more than 40 mm in any direction from the midline of the jugum sphenoidale. Symon et al. also considered giant adenomas to be tumors extending within 6 mm of the foramen of Monro. Others considered adenomas with suprasellar extension of Hardy grades C and D as being large or giant. Mohr et al. felt that having a superior margin more than 20 mm above the jugum sphenoidale was the key to identifying giant adenomas. More recently, Goel et al. defined giant adenomas as those with greater than 4 cm in maximum diameter, further subclassifying them into four grades according to invasion and patterns of extension. Despite definitional variations, all of the authors agree that very large tumors are difficult to treat by surgery alone and that adjuvant therapy is necessary.

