11.4 Patient Accrual and Study Duration

11.4.1 It is expected that it will take approximately three to five years to complete the study. The analysis for tumor shrinkage will be carried out after each follow-up and collectively after each patient has had 365 days (i.e., 12 months) of follow-up. Study-related data will be stored for 5 years after termination of the study when accrual is no longer taking place and all patients have discontinued follow-up procedures. Blood drawn for translation research will be kept indefinitely or until exhausted.

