11.5 Analysis Plan

11.5.1 Interim Reports

11.5.1.1 Interim reports will be updated at least every six months until the results of the study are published. In general, the interim reports will contain information about patient accrual rate with projected completion dates of the trial, status of QA review and compliance rate of treatment per protocol, and the frequencies and severity of toxicity.

11.5.1.2 *The Analysis of Tumor Shrinkage:* This analysis will be carried out when each patient has had at least 730 days (i.e., 24 months) of follow-up. The percent change in size and volume of the adenoma will then be calculated by subtracting the post-treatment measurements from the pre-treatment measurements then divided by the pre-treatment measurements and then multiplied by 100. The mean, median and standard deviation of the percent change will be determined.

11.5.1.3 *Estimation of Secondary Endpoints Related to the Efficacy:* Cumulative incidence approach will be used to estimate the progression free survival. For any individual patient, progressive disease (PD) within the treated lesion will be scored as PD for that patient

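### The primary response rate has no fixed denominator or analysis time, could count shrinkage after other treatment, and carries a stated 87% power that no exact cut-off delivers

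*Combined protocol and SAP*

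**What the plan says.** **Denominator.** Section 11.3.2 names as the determinant of sample size "The predicted partial or complete response rate (PR+CR) of treated subjects at a follow-up interval of 12 months". The same paragraph sets 10% as too low and 50% as worthwhile, and claims 87% power with 10 patients at alpha 0.025. It then raises enrolment so that enough patients are evaluable: "allowing for a small number of patients who would be lost to follow-up or otherwise found non evaluable, a total of up to 12". This applies to each of the two cohorts. *Evaluable* occurs only here and is not defined. The test and its sidedness are not stated.

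**Timing.** Sections 2.1.1 and 11.1.1 both define response within 12 months. Section 11.4.1 analyses shrinkage after each follow-up and "collectively after each patient has had 365 days". Section 11.5.1.2 says of the shrinkage analysis: "This analysis will be carried out when each patient has had at least 730 days". Neither gives a rule for a patient who dies or is lost before then.

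**Response formula.** Section 11.1.1 computes percent change by "subtracting the post-treatment measurements from the pre-treatment measurements then divided by the pre-treatment measurements", times 100. It places no condition on treatment given between the two scans.

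**Other treatment.** The Synopsis states: "Eligible patients may have a functioning or non-functioning adenoma". Section 1.1.1 says of secretory tumours: "First-line therapy can be either medical or surgical depending on the hormone being secreted". Section 7.2.1 covers supportive therapy only. Appendix VI assumes hormone therapy and chemotherapy as salvage for recurrence, but only to cost them. The one scoring rule for progression ("progressive disease (PD) within the treated lesion will be scored as PD for that patient") sits in 11.5.1.3 under progression-free survival.

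**The concern.** Each cohort has 10 to 12 patients and a formal 10% against 50% criterion, so one or two patients move the estimate visibly and can decide the test. Three things are left to be settled after the data are known:

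- whether patients without full follow-up stay in the denominator;
- whether the 365-day or the 730-day analysis is the primary one;
- whether a scan taken after another tumour-directed treatment can establish a response to the implant.

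The third choice can only raise the rate. The first can move it either way. In addition, the stated power is the only guide to how the test will be run, and it does not identify a cut-off.

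**Working it through.** **Inputs from 11.3.2:** p0 = 0.10, p1 = 0.50, n = 10 (up to 12 enrolled) per cohort, alpha 0.025, stated power 87%. The plan names no test; a one-sided exact binomial test is assumed below.

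**1. The plan's 87%.** For cut-off r, alpha = P(X ≥ r | n, 0.10) and power = P(X ≥ r | n, 0.50).

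| Cut-off | Alpha | Power |
|---|---|---|
| 3/10 | 0.0702 | 94.5% |
| 4/10 | 0.0128 | 82.8% |
| 4/11 | 0.0185 | 88.7% |
| 4/12 | 0.0256 | 92.7% |
| 5/12 | 0.0043 | 80.6% |

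At n=10 the smallest cut-off that respects 0.025 is 4, with power 848/1024 = 82.8%. No exact cut-off at n=10 gives 87%.

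Normal approximations come closer. With se0 = √(0.09/10) = 0.0949 and se1 = √(0.25/10) = 0.1581:

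- two-sided 0.025, uncorrected: Φ((0.40 − 2.241 × 0.0949)/0.1581) = 88.2%;
- one-sided 0.025, continuity-corrected: Φ((0.40 − 1.960 × 0.0949 − 0.05)/0.1581) = 85.0%.

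Both are within 2 points of 87%, so an approximation is the likely source. Both still imply a cut-off of 4 at n=10, where the exact power is 82.8%.

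**2. Effect of the denominator on the estimate.** Take 5 responders among 12 implanted and two patients left out, which is the plan's own allowance of 12 − 10:

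- all implanted: 5/12 = 41.7%;
- two failures left out: 5/10 = 50.0%, a difference of 8.3 points;
- two early responders left out: 3/10 = 30.0%, a difference of 11.7 points.

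**3. Effect of the denominator on the test.** Leaving out failures changes the exact result only at exactly 4 of 12: p = 0.0256, against 0.0185 for 4/11 and 0.0128 for 4/10. If failures were always the ones left out, the false-positive rate would be at most 0.0256, which is 0.0006 above 0.025. With two random losses at a true 10%, the chance of this flip is P(X=4 | 12) × C(8,2)/C(12,2) = 0.0213 × 28/66 = 0.9%. Under both approximations in step 1 the cut-off is 4 at n = 10, 11 and 12, so leaving out failures never flips the test. Leaving out two early responders turns 5/12 (p=0.0043) into 3/10 (p=0.070).

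**4. Other treatment.** One non-responder scored as a responder turns 3/10 (p=0.070) into 4/10 (p=0.0128). The documents give no frequency. As an assumption, suppose k of 10 are scored this way and the others respond at 10%. P(X ≥ 4−k | 10−k, 0.10) is then 1.3%, 5.3% or 18.7% for k = 0, 1 or 2. This is a worst case, since all k must shrink by more than 30% by month 12.

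**5. Power if all implanted patients are analysed.** With cut-off 5/12 and a 50% rate among those followed, P(X ≥ 5) with n = 12, 11 or 10 is 80.6%, 72.6% or 62.3% for none, one or two patients lost without a documented response.

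**The case against.** This is a small pilot, and the denominator hardly affects the test: step 3 shows a flip at a single outcome, and only under an exact test that the plan does not name. That stands, and the false-positive rate is not the reason to act.

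A reader might set 50.0% beside 30.0% and infer a 20-point range for the same patients. The documents do not support that. The two figures come from different loss patterns, and who is lost is a fact rather than an analysis choice. For a fixed pair of losses the gap is 8.3 or 11.7 points.

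The 11.7-point case is itself weak. Section 11.1.1 counts any response occurring within a year and scans are every three months, so a documented early responder already meets the endpoint. Dropping that patient requires the 12-month wording of the sample-size section to override the endpoint definition. Also, 12 is a ceiling on enrolment; patients enrolled but not implanted might be the non-evaluable ones, so 12 implanted with two lost is an assumption.

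On other treatment, a reader might infer that the formula will inflate the rate. The documents do not say that any such treatment is expected in year 1, and the undefined non-evaluable category could be used to exclude those patients. The point rests on silence and shows only what could happen. Exclusion is also not the same as counting them as non-responders.

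Finally, the 730-day analysis may be meant as a later second look. The text does not say so.

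**Conclusion.** The point holds as a gap in specification plus a power figure that needs replacing. The primary set and the primary time point are not fixed, and for given losses the reported rate can differ by 8.3 points (or by 11.7, under a reading that conflicts with 11.1.1). The effect on the type I error is negligible. The formula could credit the implant with shrinkage after other tumour-directed treatment; how often is unknown, but one such patient would be enough to turn 3/10 into a positive result.

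The 87% is not delivered by any exact cut-off at n=10. A reader might infer that it has no basis at all, but two normal approximations come within 2 points of it. The accurate statement is that the usable rule, 4/10, has 82.8% power.

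These conclusions assume a one-sided exact test at 0.025 and, for the denominator examples, 12 implanted patients with up to two left out.

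**What to change.** - **11.3.2:** name the test (exact one-sided binomial at 0.025) and replace 87% with the cut-off and power at a true 50% for each realised n: 4/10, 82.8%; 4/11, 88.7%; 5/12, 80.6%.
- **11.1.1 and 11.3.2:** make all implanted patients in each cohort the primary set. A responder is anyone with a documented volume reduction above 30% on a scan up to the month-12 visit and before any other tumour-directed treatment. Define that term for analysis purposes only, including whether drug treatment of a functioning adenoma falls under it. Documented responders who are later lost remain responders; everyone else is a non-responder. Report the evaluable-only rate, with *evaluable* defined, as a sensitivity analysis.
- **11.4.1 and 11.5.1.2:** reconcile them so that the 12-month analysis is primary, and state the role of the 730-day one.

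**Cost.** No extra patients or scans are needed. The reported rate may be slightly lower, and counting otherwise-treated patients as non-responders may understate the implant's effect. Power at 5/12 is 80.6% with none lost, and at worst 72.6% or 62.3% with one or two lost without a documented response; the cap of 24 patients prevents buying it back. If that is too low, the plan could state 4/12 in advance (92.7%, 88.7% or 82.8% with none, one or two lost), while declaring openly that its alpha of 0.0256 exceeds 0.025.
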